#### **9.2.7 BLEED Population**

The BLEED population will include all documented bleeding episodes treated with *Octafibrin* in subjects of the FAS.

#### **9.2.8 BLEED-PP Population**

A BLEED-PP population comprising bleeding episodes with no major protocol deviations will be defined in the SAP, with criteria similar to the FirstBLEED-PP population.

#### **9.2.9 SURG population**

The SURG population will include all surgical interventions with a need for at least one infusion of the IMP during the time period from the day of surgery until overall clinical assessment of haemostatic efficacy (third inclusion criterion; see Section 4.2) in subjects of the FAS.

A SURG-PP population comprising surgical interventions with no major protocol deviations will be defined in the SAP with criteria similar to the FirstBLEED-PP population.

**NOTE:** Any protocol deviations which will lead to the exclusion from an analysis population other than those mentioned above must be agreed upon in writing by the Sponsor and the study statistician, and in any case, before database closure.

The efficacy analysis for the primary endpoint will be performed with the data from the first bleeding event of each patient using the FirstBLEED population (ITT analysis) as the primary population and using the FirstBLEED-PP population (PP analysis) as a secondary population. An additional analysis will be performed for all bleeding events on the BLEED and BLEED-PP population. The primary analysis population for the PK analysis will be the PK-PP population.

#### **9.2.10 Subpopulations**

Subpopulations based on the following categories will be examined:

- Severity of bleeding: minor versus major (subpopulations of the BLEED population)
- Age 0 to  $<6$  years versus 6 to  $<12$  years

## 9.3 Efficacy Analysis Plan

### 9.3.1 Primary Endpoint

The primary endpoint is the overall clinical assessment of haemostatic efficacy of *Octafibrin* in treating the first documented bleeding episode of each patient (FirstBLEED population). The first bleeding episode covers the time period from the first *Octafibrin* infusion until 24 hours (i.e., 1 day) after the last infusion or the end of the treatment observation period, whichever comes last (see Section 3.1.1). The final efficacy assessment of each patient will be adjudicated by an Independent Data Monitoring & Endpoint Adjudication Committee (IDMEAC).

Frequency distribution will be provided for the haemostatic efficacy scale data. In addition, the assessment made by the investigator on the 4-point rating scale will be transformed to a dichotomous endpoint with success defined as a rating of ‘excellent’ or ‘good’. A 2-sided 95% CI for the success rate in haemostatic efficacy (‘excellent’ or ‘good’) according to Clopper/Pearson will be computed.

For the following subjects, the haemostatic efficacy outcome will be set to the worst efficacy category, i.e., ‘none’:

- Subjects who withdraw from the study due to lack of efficacy
- Subjects receiving cryoprecipitate or concentrates containing fibrinogen other than the IMP between first infusion and efficacy assessment (unless it is clearly documented that these products were administered for reasons unrelated to IMP efficacy [e.g., pharmacy error])
- Subjects with missing haemostatic efficacy assessment

Haemostatic efficacy will be displayed by covariates (sex, age groups, weight, type of bleeding) in tables or with covariates in listings depending on the number per subgroup.

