### **Primary endpoint**

The primary endpoint is the overall clinical assessment of the haemostatic efficacy of *Octafibrin* in treating the first documented bleeding episode of each patient. The first bleeding episode covers the time period from the first *Octafibrin* infusion for the treatment of a bleeding episode until 24 hours (i.e., 1 day) after the last infusion or the end of the treatment observation period, whichever comes last.

For the analysis, the assessment made by the investigator on the 4-point rating scale will be transformed to a dichotomous endpoint with success defined as a rating of excellent or good. The final efficacy assessment of each patient will be adjudicated by an Independent Data Monitoring & Endpoint Adjudication Committee (IDMEAC). Bleeding efficacy data will be summarised using descriptive statistics and displayed graphically, differentiating between the first bleeding episode per patient (primary endpoint) and all bleeding episodes (secondary endpoint).

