**Table 4: Algorithm for the adjudicated intra- and post-operative assessments of haemostatic efficacy**

Intra-operative assessment	Post-operative assessment			
	Excellent	Good	Moderate	None
Excellent	Success	Success	Success	Primary adjudication
Good	Success	Success	Primary adjudication	Failure
Moderate	Success	Primary adjudication	Failure	Failure
None	Primary adjudication	Failure	Failure	Failure

Outcomes designated as 'primary adjudication' will be assigned following adjudication by the IDMEAC.

In documenting the adjudication process for the assessment of surgical prophylaxis, the IDMEAC will explicitly identify any subjects for whom they considered there to be 'unexpected blood loss due to surgical complications' and state whether this unexpected blood loss altered the 4-point assessment of surgical prophylaxis. Any such cases will be analyzed both including (as a sensitivity analysis) and excluding the unexpected blood loss.

In the event that any intra- or post-operative endpoint data differ between the investigator's assessment and the adjudicated assessment by the IDMEAC, the endpoint will be that based on the adjudicated assessments. The efficacy of *Octafibrin* in surgical prophylaxis will be evaluated by descriptive statistics based on an overall assessment.

In addition, the location, severity, and type of surgery will be documented. Expected and actual duration of surgical procedure and details of administered dose(s) of *Octafibrin* (pre-, intra- and/or post-operatively) will be recorded. Fibrinogen plasma levels (pre-, intra-, and post-operatively) will be measured. Details of concomitantly administered products (except standard anaesthesia), along with a brief narrative describing the outcome of the intervention, will be recorded.

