## **8.8 Independent Data Monitoring & Endpoint Adjudication Committee**

An Independent Data Monitoring & Endpoint Adjudication Committee (IDMEAC) will be established by the Sponsor. The IDMEAC will be composed of recognised experts in the field of clinical care who are not actively recruiting subjects.

The IDMEAC will review relevant data periodically during the study and will give advice on the continuation, modification, or termination of the study. This committee will also be responsible for adjudicating the primary and secondary efficacy endpoints in the study.

A IDMEAC charter will define in detail the composition, responsibilities and procedures of the IDMEAC.

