#### 4-point haemostatic efficacy scale

Category	Definition
Excellent	Immediate and complete cessation of bleeding in the absence of other haemostatic intervention as clinically assessed by the treating physician; and/or <10% drop in haemoglobin compared to pre-infusion.
Good	Eventual complete cessation of bleeding in the absence of other haemostatic intervention as clinically assessed by the treating physician; and/or <20% drop in haemoglobin compared to pre-infusion.
Moderate	Incomplete cessation of bleeding and additional haemostatic intervention required, as clinically assessed by the treating physician; and/or between 20 and 25% drop in haemoglobin compared to pre-infusion.
None	No cessation of bleeding and alternative haemostatic intervention required, as clinically assessed by the treating physician; and/or >25% drop in haemoglobin compared to pre-infusion.

The final efficacy assessment of each patient will be adjudicated by the Independent Data Monitoring & Endpoint Adjudication Committee (IDMEAC).

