**Algorithm for the adjudicated intra- and post-operative assessments of haemostatic efficacy**

Intra-operative assessment	Post-operative assessment			
	Excellent	Good	Moderate	None
Excellent	Success	Success	Success	Primary adjudication
Good	Success	Success	Primary adjudication	Failure
Moderate	Success	Primary adjudication	Failure	Failure
None	Primary adjudication	Failure	Failure	Failure

Outcomes indicated 'Primary adjudication' will be assigned following adjudication by the IDMEAC ('primary adjudication').

In the event that any intra- or post-operative endpoint data differ between the investigator's assessment and the adjudicated assessment by the IDMEAC, the endpoint will be that based on the adjudicated assessments.

The IDMEAC will conduct an independent adjudication of all haemostatic efficacy results and adjudicate the investigator's assessments of the intra- and post-operative assessments ('secondary adjudication').

In addition, the location, severity, and type of surgery will be documented. Expected and actual duration of surgical procedure and details of administered dose(s) of Octafibrin (pre-, intra- and/or post-operatively) will be recorded. Fibrinogen plasma levels (pre-, intra-, and post-operatively) will be measured. Details of concomitantly administered products (except standard anaesthesia), along with a brief narrative describing the outcome of the intervention, will be recorded.

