### 10.1 Treatment of first bleeding episode

The first bleeding episode covers the time period from the first *Octafibrin* infusion until 24 hours (i.e., 1 day) after the last infusion or the end of the treatment observation period, whichever comes last

Haemostatic efficacy will be displayed by covariates (sex, age groups, weight, and type of bleeding) in tables or with covariates in listings depending on the number per subgroup.

The following will be presented following the manners of presentation described in section 7:

- Number of subjects with at least one bleeding episode
- Type of first bleeding episode (spontaneous, traumatic, post-operative, other)
- Site of first bleeding episode
- The duration of the first bleeding episode will be calculated.  
If the end time of a bleeding episode is missing it will be set to 23:59 of the same day, if the start time of a bleeding episode is missing it will be set to 0:00 of the same day.
- Severity of the first bleeding episodes (mild, moderate, severe)
- Efficacy assessment of the treatment made by the investigator (excellent, good, moderate, none) for the first bleeding episode.

For the following subjects, the haemostatic efficacy outcome will be set to the worst efficacy category, i.e., 'none':

- Subjects who withdraw from the study due to lack of efficacy during or after the first bleeding episode
- Subjects receiving cryoprecipitate or concentrates containing fibrinogen other than the IMP between first infusion and efficacy assessment for the first bleeding episode (unless it is clearly documented that these products were administered for reasons unrelated to IMP efficacy [e.g., pharmacy error])
- Subjects with missing haemostatic efficacy assessment after the first bleeding episode
- In addition to the four points scale the proportion of first bleeding episodes successfully treated with *Octafibrin* will be evaluated. "Successfully treated" are all "excellent" and "good" efficacy ratings of treated bleeding episodes. A two-sided 95% CI for the success rate in haemostatic efficacy ('excellent' or 'good') according to Clopper/Pearson will be computed.
- Treatment details: number of exposure days, number of injections, dosing incl. batch numbers., consumption of *Octafibrin* (IU/kg) for the first bleeding episode will be listed

- Any haemostatic co-medication will be listed.

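### The primary first-bleed success rate is taken from the investigator's rating, and no rule says which rating counts when the planned IDMEAC adjudication differs

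*Protocol*

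**What the plan says.** **Source of the success rate.** Protocol 9.3.1 says that "the assessment made by the investigator on the 4-point rating scale will be transformed to a dichotomous endpoint", with success meaning excellent or good, and attaches a two-sided 95% Clopper-Pearson interval. The statistical part of the protocol synopsis has the same rule: "For the analysis, the assessment made by the investigator on the 4-point rating scale will be transformed to a dichotomous endpoint". SAP 10.1 lists "Efficacy assessment of the treatment made by the investigator (excellent, good, moderate, none) for the first bleeding episode", then defines the success proportion and its interval. It does not mention the IDMEAC.

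**Adjudication of the same endpoint.** Protocol 9.3.1 also provides for IDMEAC adjudication of every patient's final assessment, as do the synopsis, Protocol 3.1.1 and 7.2.1, and SAP 4.3.1. On the committee's remit, Protocol 8.8 says: "This committee will also be responsible for adjudicating the primary and secondary efficacy endpoints in the study".

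**What the SAP does with adjudicated bleed ratings.** SAP 10.4 (all bleeds) shows them beside the investigator's, and Table 14.2.20 summarises both. Table 14.2.12 reports a final outcome for the first bleed without saying whose rating it is.

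**Surgery.** Where the two ratings of intra- or post-operative data differ, SAP 4.3.6 says "the endpoint will be that based on the adjudicated assessments". Protocol 7.2.2.4 has the same rule. Protocol 9.3.2.5 and SAP 10.5 base the primary surgical analysis on adjudicated assessments.

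**The concern.** The plan sets up independent adjudication of its primary endpoint but does not connect it to the primary result. The secondary surgical endpoint, with a minimum of 2 procedures, has a precedence rule; the primary endpoint has none. A programmer working from Protocol 9.3.1 and SAP 10.1 would use the investigator's rating. One working from the word final in Table 14.2.12 could use the committee's.

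There is no control arm and no test, so the category counts, the success rate and its interval are the primary result. If their source is not fixed before the ratings are known, the choice can be made after both are on the table.

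Disagreement is plausible from the scale itself. Protocol Table 2 joins clinical cessation and haemoglobin drop by and/or. A bleed that stopped only incompletely and needed further intervention, but with a haemoglobin drop under 10%, meets wording in both the moderate and the excellent rows. Two careful raters could land on opposite sides of the success boundary.

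**Working it through.** The plan gives no sample-size, power or discordance figure, so there is no stated number to reproduce. The check has two parts.

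**1. Is there a rule for bleeds anywhere?**

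| Place | Rater named | Rule if ratings differ |
|---|---|---|
| Protocol synopsis and 9.3.1, success rate | Investigator | None |
| Protocol synopsis, 3.1.1, 7.2.1, 9.3.1; SAP 4.3.1, final assessment | IDMEAC adjudicates | None |
| SAP 10.1, first bleed | Investigator | None |
| SAP 10.4 and Table 14.2.20 | Both, displayed | None |
| Table 14.2.12, final outcome | Not named | None |
| Protocol 7.2.2.4, SAP 4.3.6, surgery | Adjudicated | Adjudicated prevails |

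The only precedence rule is worded for intra- and post-operative data and does not reach bleeds.

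**2. How much could one differing call matter?**

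Inputs: at least 6 first bleeds (Protocol 9.1); success is excellent or good; two-sided 95% Clopper-Pearson interval (Protocol 9.3.1). Assumption: one bleed is rated on opposite sides of the good/moderate boundary.

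- Shift in the rate: 100/6 = 16.7 points.
- 6/6: the lower limit solves p^6 = 0.025, so p = 0.025^(1/6) = 0.541. Interval 54.1 to 100%.
- 5/6: the lower limit solves 6p^5(1−p) + p^6 = 0.025, giving 0.359; the upper limit solves 1 − p^6 = 0.025, giving 0.996. Interval 35.9 to 99.6%.
- The lower limit falls 54.1 − 35.9 = 18.2 points.
- 4/6, by the same method: 22.3 to 95.7%.

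If all 12 PK patients had a treated bleed (an assumption), the shift is 100/12 = 8.3 points: 12/12 (73.5 to 100%) against 11/12 (61.5 to 99.8%).

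The chance of at least one success/failure disagreement among 6 bleeds is 1 − (1 − d)^6, for an assumed independent disagreement probability d per bleed:

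- d = 5%: 26.5%
- d = 10%: 46.9%
- d = 20%: 73.8%

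These values of d are a range for illustration; the documents support none in particular.

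**The case against.** The strongest reply is that the plan can be run as written. The investigator's rating is the stated source, both ratings will be displayed, and with about six first bleeds any disagreement should be visible. The study is descriptive (Protocol 9; SAP 7), so no error rate or success threshold depends on the choice. All of that stands, and it limits the seriousness of the point. It does not supply the missing link: no listed output is specified as an adjudicated first-bleed rate with its interval.

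A second reply is that final already means adjudicated, since Table 14.2.20 attaches that word to the IDMEAC and Table 14.2.12 uses it too. This is a fair reading, but it contradicts the instruction to dichotomise the investigator's rating. A third is that the IDMEAC charter may settle it. The charter is not available here, and Protocol 8.8 describes it as covering composition, responsibilities and procedures. SAP 2 undertakes to describe all analyses in full.

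Three stronger readings are tempting and not supported:

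- A reader might infer that the all-bleeds endpoint has the same gap. It does not: the synopsis and Protocol 3.1.2.2 define it expressly by the investigator's assessment.
- A reader might quote intervals for age groups of 3. SAP Table 14.2.13, which carries the interval, has no age-group tag, and SAP 10 stratifies only where appropriate, so those intervals are not a specified output.
- A reader might infer that the investigator's rating inflates success. The documents give neither the rate nor the direction of disagreement.

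**Conclusion.** The point holds for the first-bleed primary endpoint. Protocol 9.3.1 and SAP 10.1 take the result from the investigator, adjudication of the same endpoint is planned, and no rule joins the two. The sponsor's surgery rule shows what such a rule looks like.

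With 6 bleeds and one discordant call, the rate moves 16.7 points and, from 6/6 to 5/6, the lower limit moves 18.2 points. Both figures rest on the assumed discordance; the effect is nil if the raters agree and smaller if more than 6 children bleed. It is not established that the reported rate will be wrong or biased, only that its source is stated one way and implied another. This should be fixed before the ratings are analysed, but it does not threaten the study.

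**What to change.** **Primary endpoint.** In the protocol synopsis, Protocol 9.3.1 and SAP 10.1, state that the four-category distribution, the success rate and its Clopper-Pearson interval use the IDMEAC-adjudicated category of the first bleeding episode, and that this category is used wherever it differs from the investigator's. This follows the surgery rule. Report the investigator-based rate and interval as a sensitivity analysis, with an investigator-by-IDMEAC cross-tabulation of first bleeds. Name the rater in the titles of Tables 14.2.12 and 14.2.13.

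**Outcomes set to none.** Keep the existing rules for withdrawal for lack of efficacy and for other fibrinogen products, and state that they override the adjudicated category. Apply the missing-assessment rule (Protocol 9.3.1 and 9.6, SAP 10.1) and the non-missing criterion of the first-bleed per-protocol set (Protocol 9.2.6, SAP 6.1) to the rating that defines the endpoint.

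**All bleeds and MCF.** Keep the investigator-based all-bleeds endpoint and add the adjudicated rate beside it. Name the rater in the clot-strength analyses split by efficacy (Protocol 9.3.2.2, SAP 10.2, Tables 14.2.18 and 14.2.19).

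**Cost.** A short protocol and SAP amendment, some relabelling, and a few small outputs. Adjudication of first bleeds is already planned. For all bleeds, confirm that every episode is adjudicated: most passages speak of each patient, and coverage of every episode rests on the general wording of Protocol 8.8 and the population of Table 14.2.20. The downside is that the primary rate may move in either direction.

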Patients should be treated with the investigational medicinal product (IMP) whenever possible. If, in the opinion of the investigator, a bleeding episode is not effectively stopped or surgical prophylaxis is not adequate after the recommended dose of *Octafibrin* has been administered, the subject may receive a different licensed fibrinogen concentrate (e.g., Haemocomplettan P®/RiaSTAP™) or whatever the investigator considers standard of care. The use of another licensed fibrinogen concentrate is also permitted in emergency situations, e.g., if the IMP is not available for the patient in time.

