**Table 2: Overall clinical assessment of haemostatic efficacy**

Category	Definition
Excellent	Immediate and complete cessation of bleeding in the absence of other haemostatic intervention as clinically assessed by the treating physician; and/or <10% drop in haemoglobin compared to pre-infusion.
Good	Eventual complete cessation of bleeding in the absence of other haemostatic intervention as clinically assessed by the treating physician; and/or <20% drop in haemoglobin compared to pre-infusion.
Moderate	Incomplete cessation of bleeding and additional haemostatic intervention required, as clinically assessed by the treating physician; and/or between 20 and 25% drop in haemoglobin compared to pre-infusion.
None	No cessation of bleeding and alternative haemostatic intervention required, as clinically assessed by the treating physician; and/or >25% drop in haemoglobin compared to pre-infusion.

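### The rule that sets rescued bleeds to None is narrower than the rescue the protocol allows, and the efficacy scale has no tie-break for the remainder, so the primary success rate could be biased upward

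*Protocol*

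**What the plan says.** **The override rule.** Protocol 9.3.1 sets the outcome to None in three cases: withdrawal for lack of efficacy, a missing assessment, and "Subjects receiving cryoprecipitate or concentrates containing fibrinogen other than the IMP between first infusion and efficacy assessment". There is an exception, "unless it is clearly documented that these products were administered for reasons unrelated to IMP efficacy". SAP 10.1 applies the same product list to the primary endpoint: "Subjects receiving cryoprecipitate or concentrates containing fibrinogen other than the IMP between first infusion and efficacy assessment for the first bleeding episode". SAP 10.4 does so for all bleeding episodes.

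**The rescue allowed.** If the investigator judges that the recommended dose has not stopped the bleed, Protocol 3.2 allows a different fibrinogen concentrate "or whatever the investigator considers standard of care". Protocol 4.4.1 and 4.8 say the same.

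**The scale.** In Protocol Table 2, repeated in SAP 4.3.1, Good reads "Eventual complete cessation of bleeding in the absence of other haemostatic intervention as clinically assessed by the treating physician; and/or <20% drop in haemoglobin". Excellent has the same structure, with immediate cessation "and/or <10% drop in haemoglobin compared to pre-infusion". Moderate reads "Incomplete cessation of bleeding and additional haemostatic intervention required, as clinically assessed by the treating physician; and/or between 20 and 25% drop in haemoglobin". None has the same form, with no cessation, an alternative intervention required, and/or a haemoglobin drop above 25%.

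**Success.** Under Protocol 9.3.1 the investigator's rating "will be transformed to a dichotomous endpoint with success defined as a rating of" Excellent or Good. The IDMEAC adjudicates the final assessment of each patient.

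**The concern.** The None rule exists so that a child whose bleed needed substitute treatment cannot be counted as a success of the IMP. Its product list is narrower than the rescue the protocol permits. Plasma is the clearest gap: Protocol 1.1 gives a normal circulating fibrinogen concentration of 2.9 to 4.5 g/L, so plasma supplies the same active protein, yet the rule does not name it. Other haemostatic treatment is not named either.

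For rescue outside the list, the outcome depends on how the 4-point scale is read, and the scale can be read two ways. The study is open-label and uncontrolled, the rating is made by the treating side, and the minimum sample is six children. Any leniency in that reading raises the success rate, and one child moves it by a sixth.

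**Working it through.** The plan states no power, alpha or expected success rate, so there is no figure to reproduce. The check is mainly textual.

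**Step 1. Apply the rule and the scale to a rescued child.** Suppose the bleed was not controlled, rescue was given, and haemoglobin fell by less than 10%.

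| Rescue given | None rule (Protocol 9.3.1, SAP 10.1) | Clinical clause of Table 2 | Haemoglobin clause of Table 2 | Outcome under the plan |
|---|---|---|---|---|
| Cryoprecipitate or another fibrinogen concentrate | Applies | Moderate or None | Excellent | None, fixed |
| Plasma | Not named | Moderate or None | Excellent | Not determined |
| Other haemostatic treatment | Not named | Moderate or None | Excellent | Not determined |

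With a drop of 10% to under 20%, the haemoglobin clause gives Good instead of Excellent, which is still a success. In the last two rows the child meets a success category and a failure category together, because the two clauses are joined by and/or and no precedence is stated.

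**Step 2. Is the conflict easy to reach?** Protocol 5.4.3 defines minor bleeds as mild joint, superficial muscle, soft-tissue or oral bleeds, and counts intraocular and intraarticular bleeds as major. Such bleeds need not lower haemoglobin much, so the haemoglobin clause can be met even when haemostasis has failed clinically.

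**Step 3. Do other provisions settle it?**
- Protocol 7.2.1 has the investigator take additional haemostatic treatment into account. That is an input to a judgement, with no stated consequence for the rating.
- The IDMEAC adjudicates, but on the same scale. Protocol 9.3.1 dichotomises the investigator's rating, SAP 10.1 tabulates the investigator's rating, and SAP 10.4 shows the adjudicated result alongside it.
- SAP 10.1 lists haemostatic co-medication but gives it no effect on the endpoint.
- The listed FirstBLEED-PP criteria (Protocol 9.2.6) exclude for fibrinogen products only in the two weeks before treatment, not during the bleed.

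**Step 4. Size, as an illustration.** Inputs: minimum n = 6 (Protocol 9.1) and the two-sided 95% Clopper-Pearson interval (Protocol 9.3.1). For x successes in n, the lower limit is the 0.025 quantile of Beta(x, n − x + 1) and the upper limit is the 0.975 quantile of Beta(x + 1, n − x). For x = n the lower limit reduces to 0.025^(1/n) and the upper limit is 1. Assume every other child is a success.

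| n | Unlisted rescue counted as success | One such child counted as failure | Two counted as failures |
|---|---|---|---|
| 6 | 6/6 = 100% (54.1 to 100) | 5/6 = 83.3% (35.9 to 99.6) | 4/6 = 66.7% (22.3 to 95.7) |
| 12 (assumed) | 12/12 = 100% (73.5 to 100) | 11/12 = 91.7% (61.5 to 99.8) | 10/12 = 83.3% (51.6 to 97.9) |

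At n = 6, one child moves the estimate by 1/6 = 16.7 percentage points and the lower limit by 54.1 − 35.9 = 18.2 points.

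**The case against.** The strongest reply is that the scale itself already treats rescue as failure. Excellent and Good refer to cessation without another haemostatic intervention. Moderate and None are defined by needing one, whatever the product. On this view the None rule is only an extra override for substitute fibrinogen, and plasma given for an uncontrolled bleed fits Moderate or None on its plain clinical meaning. The assessor must weigh additional treatment, the IDMEAC adjudicates, and co-medication is listed by episode. With about six children, a rescued child rated a success would be visible.

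Much of this stands. A reader might infer that any child rescued outside the list automatically counts as a success, or that such rescue is ignored. The documents do not support that: the clinical clause points the other way, and success requires a rater to rely on haemoglobin. What remains is that the plan permits that reading and nothing in it forbids it.

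A reader might also see a contradiction between the None rule and the wider wording on fibrinogen-containing blood products in the eligibility and per-protocol criteria. Those criteria serve a pre-treatment washout, so the difference in wording is not itself an inconsistency. It shows only that a wider term was available. Nor do the documents name plasma as rescue; it falls under the open standard-of-care allowance.

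Finally, the analysis is descriptive with no success threshold, so no formal decision turns on one child.

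**Conclusion.** The point holds as a gap in endpoint derivation that should be closed. Success after unlisted rescue is possible, not automatic, and the plan leaves it to judgement where a fixed rule was evidently intended. Any resulting bias in the primary success rate would be upward.

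The illustrated size is 16.7 percentage points per child at n = 6. It assumes that a child receives rescue outside the list, is rated on haemoglobin despite the clinical clause, and keeps that rating for the success rate. The documents give no frequency for any of these, so the figures show sensitivity and do not estimate the bias.

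It would go too far to conclude that every other haemostatic intervention should be set to None. Table 2 defines Moderate by the need for additional intervention, so that rule would empty Moderate of its clinical meaning and distort the four-category distribution, which is itself a planned output.

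**What to change.** Two changes, both to how the endpoint is derived. Neither bears on which rescue treatment is given.

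1. In Protocol 9.3.1 and SAP 10.1 and 10.4, extend the None rule from cryoprecipitate and concentrates to any fibrinogen-containing product other than the IMP, including plasma. Keep the exception for clearly documented unrelated use.
2. In Protocol Table 2 and SAP 4.3.1, state that any other haemostatic intervention given because bleeding was not controlled overrides the haemoglobin clause. Such an episode cannot be rated Excellent or Good, and is rated Moderate or None under the clinical definitions.

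The cost is a wording change in both documents. Concomitant medication is already recorded throughout each 30-day follow-up, and haemostatic co-medication is already listed, so no new data item is proposed. The reported success rate may be slightly lower.
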